Abbreviations: ADA = antidrug antibodies; CIC = circulating immune complexes; CRU = Clinical Research Unit; ECG = electrocardiogram; EOI = end of infusion; ET = early termination; FcRn = neonatal crystallizable fragment receptor; h = hours; ICF = informed consent form; Ig = immunoglobulin; NA = not applicable; OP = outpatient; PD = pharmacodynamic(s); PE = physical examination; PK = pharmacokinetic(s); WOCBP = women of childbearing potential.

<sup>b Serum pregnancy test at Screening and Day -1 and urine pregnancy test for all other timepoints in CRU and OP.

<sup>c For the Day 141 Visit, dispense a urine pregnancy test kit for the Day 169 Follow-up Phone Call. For an ET Visit, dispense urine pregnancy test kits to allow monthly testing for 3 months after the last dose.

<sup>d Participants will be requested to take a urine pregnancy test at home at approximately Day 169, or if ET, monthly for 3 months after the last dose; the site will solicit pregnancy test results, along with adverse events and concomitant medications, via phone call.

<sup>e Full PE at screening and symptom directed PE thereafter.

 $^{\rm f}\,$  Fasting, due to lipid panel. Note: lipid panel is not performed at Screening.

 $^{\rm g}\,$  Visit window (hours) is not applicable for urinalysis.

<sup>h Including temperature, respiratory rate, and pulse oximetry.

 Table 10:
 SoA – Screening Through Day 7 for Multiple-Dose Cohorts 4 to 6

Study Day	Screening	-1			1			2	3	4	5	6	7
Assessments	Day -60 to Day -2	Admit	Pre- dose	EOI	2 h a	4 h a	12 h a	24 h a	48 h	72 h	96 h	120 h	144 h
Window (hours)			NA	+0.25	±0.25	±0.5	±0.5	±1	±1	±1	±1	±1	±1
Status (CRU or OP)	OP						C	RU					
Informed consent	X												
Inclusion/exclusion criteria	X	Xb											
Pregnancy test (WOCBP) c	X	X											
FSH test (postmenopausal women)	X												
Alcohol breath test	X	X											
Urine drug screen	X	X											
Hepatitis B and C screen	X												
Evidence of vaccination d	X	Xb											
HIV (types 1 and 2) screen	X												
Medical history and demographics	X	Xb											
Physical examination e	X		X										
Height, weight, and BMIf	X		X										
Randomization			X										
Study drug administration			X										
PK blood sampling			X		X	X	X	X	X	X	X	X	X
PD blood sampling - IgA, IgM,	X		X		X	X	X	X	X	X	X	X	X
IgG													
PD blood sampling - IgG subtypes 1-4			X		X	X	X	X	X	X	X	X	X
PD blood sampling – CIC			X		X	X	X	X	X	X	X	X	X
Immunogenicity blood sampling - ADA			X										
FcRn occupancy			X		X		X	X	X	X		X	
Biochemistry g	X	X						X					
Coagulation	X	X						X					
Hematology	X	X						X		X			
Exploratory biomarker sample		X								X			
Urinalysis h	X	X						X		X			
Vital signs i	X	X	X	X	X	X	X	X	X	X	X	X	X
12-lead ECG (triplicate)	X	X	X	X	X	X	X	X	X	X	X	X	X
Infusion site evaluation				X	X	X	X	Xk					
Concomitant medications		1						signed at S	creening)-	 	l .	1	1
Adverse events								signed at S					

a Postdose evaluations at the 2-hour, 4-hour, 12-hour, and 24-hour timepoints are to be completed based on the start of infusion time. When multiple procedures are scheduled to occur at the same time, the following order of events should be strictly adhered to whenever possible: ECG, vital signs, blood sampling, and study intervention administration.

- b Activities will be performed on Day -1 only.
- c Serum pregnancy test at Screening and Day -1 and urine pregnancy test for all other timepoints in CRU.
- d All participants must be vaccinated as described in Section 6.5.3.
- e Full PE at screening and symptom directed PE thereafter.
- f Height and BMI at Screening only.
- g Fasting, due to lipid panel. Note: lipid panel is not performed at Screening.
- h Visit window (hours) is not applicable for urinalysis.
- i Including temperature, respiratory rate, and pulse oximetry.
- In the event of an IRR, it is recommended to collect a blood sample for assessment of tryptase, histamine, CRP, cytokines, and complement as soon as the IRR is observed (prior to administering any IRR medication), and 2 hours, 24 hours and 7 days (prior to the next dose of study drug) after onset of the IRR; a blood sample for PK/PD and ADAs may be collected if there is no predefined sample collection on the same day.
- k IRR evaluation will continue until the reaction is fully resolved.

Abbreviations: ADA = antidrug antibodies; BMI = body mass index; CIC = circulating immune complexes; CRP = C-reactive protein; CRU = Clinical Research Unit; ECG = electrocardiogram; EOI = end of infusion; FcRn = neonatal crystallizable fragment receptor; FSH = follicle stimulating hormone; h = hours; HIV = human immunodeficiency virus; ICF = informed consent form; Ig = immunoglobulin; IRR = infusion related reaction; NA = not applicable; OP = outpatient; PD = pharmacodynamic(s); PE = physical examination; PK = pharmacokinetic(s); WOCBP = women of childbearing potential.

Table 11: SoA – Day 8 Through Day 23 for Multiple-Dose Cohorts 4 to 6

Study Day		8		9a	14		15		16 a	21			22			23
Assessments	Pre- dose	EOI	2 h b	24 h b	Admit	Pre- dose	EOI	2 h b	24 h b	Admit	Pre- dose	EOI	2 h b	4 h b	12 h b	24 h b
Window (hours)	NA	+0.25	±0.25	±1		NA	+0.25	±0.25	±1		NA	+0.25	±0.25	±0.5	±0.5	±1
Status (OP or CRU)								CRU								
Pregnancy test (WOCBP) c					X					X						
Alcohol breath test					X					X						
Urine drug screen					X					X						
Physical examination d	X					X					X					
Weight	X					X					X					
Study drug administration	X					X					X					
PK blood sampling	X					X					X	X	X	X	X	X
PD blood sampling - IgA, IgM, IgG	X					X					X	X	X	X	X	X
PD blood sampling - IgG subtypes 1-4	X					X					X	X	X	X	X	X
PD blood sampling – CIC	X					X					X	X	X	X	X	X
Immunogenicity blood sampling - ADA						X										
FcRn occupancy	X					X					X	X	X		X	X
Biochemistry e					X					X						
Hematology				X	X				X	X						X
Urinalysis f					X					X						
Vital signs g	X	X	X	X	X	X	X	X	X	X	X	X	X	X	X	X
12-lead ECG (triplicate)	X					X					X	X	X	X	X	X
Infusion site evaluationh		X	Xi	X			X	Xi	X			X	X	X	X	Xi
Concomitant medications		•			·	-Monito	r continuousl		CF is sign	ed at Scree	ning)→			•		
Adverse events							r continuousl									

<sup>a Participant will be discharged from the CRU after completing all Day 9, 16, and 29 assessments.

<sup>b Postdose evaluations at the 2-hour, 4-hour, 12-hour, and 24-hour timepoints are to be completed based on the start of infusion time. When multiple procedures are scheduled to occur at the same time, the following order of events should be strictly adhered to whenever possible: ECG, vital signs, blood sampling, and study intervention administration.

<sup>c Serum pregnancy test at Screening and Day -1 and urine pregnancy test for all other timepoints in CRU.

<sup>d Full PE at screening and symptom directed PE thereafter.

<sup>e Fasting, due to lipid panel. Note: lipid panel is not performed at Screening.

<sup>f Visit window (hours) is not applicable for urinalysis.

<sup>g Including temperature, respiratory rate, and pulse oximetry.

- h In the event of an IRR, it is recommended to collect a blood sample for assessment of tryptase, histamine, CRP, cytokines, and complement as soon as the IRR is observed (prior to administering any IRR medication), and 2 hours, 24 hours and 7 days (prior to the next dose of study drug) after onset of the IRR; a blood sample for PK/PD and ADAs may be collected if there is no predefined sample collection on the same day.
- i IRR evaluation will continue until the reaction is fully resolved.
- Abbreviations: ADA = antidrug antibodies; BMI = body mass index; CIC = circulating immune complexes; CRP = C-reactive protein; CRU = Clinical Research Unit; ECG = electrocardiogram; EOI = end of infusion; FcRn = neonatal crystallizable fragment receptor; h = hours; ICF = informed consent form; Ig = immunoglobulin; IRR = infusion related reaction; NA = not applicable; OP = outpatient; PD = pharmacodynamic(s); PE = physical examination; PK = pharmacokinetic(s); WOCBP = women of childbearing potential.

Table 12: SoA – Day 24 Through Day 85 for Multiple-Dose Cohorts 4 to 6

Study Day	24	25	26	27	28	29ª	36	50	64	78	85/ET	Day 113 Follow-up Phone Call
Assessments	48 h	72 h	96 h	120 h	144 h	168 h	NA	NA	NA	NA	NA	NA
Window (CRU = hours; OP = days)	±1 h	±1 h	±1 h	±1 h	±1 h	±1 h	±1 day	±1 day	±1 day	±1 day	±1 day	±3 days
Status (OP or CRU)				CRU						OP		
Pregnancy test (WOCBP) b								X			Xc	X d
Physical examination e		X				X					X	
Weight		X				X					X	
PK blood sampling	X	X	X	X	X	X	X	X	X	X	X	
PD blood sampling - IgA, IgM, IgG	X	X	X	X	X	X	X	X	X	X	X	
PD blood sampling - IgG subtypes 1-4	X	X	X	X	X	X	X	X	X	X	X	
PD blood sampling – CIC	X	X	X	X	X	X	X	X	X	X	X	
Immunogenicity blood sampling - ADA						X		X	X		X	
FcRn occupancy	X	X		X			X	X				
Biochemistry f		X						X			X	
Coagulation		X									X	
Hematology		X						X	X		X	
Exploratory biomarker sample		X									X	
Urinalysis		Xg							X		X	
Vital signs h	X	X	X	X	X	X	X	X	X	X	X	
12-lead ECG (triplicate)	X	X	X	X	X	X					X	
Concomitant medications			•	•	←Mon	itor continuo	ously (after I	CF is signed	at Screenin	g)→	•	
Adverse events					←Mon	itor continuo	ously (after I	CF is signed	at Screenin	g)→		

<sup>a Participant will be discharged from the CRU after completing all Day 9, 16, and 29 assessments.

<sup>b Serum pregnancy test at Screening and Day -1 and urine pregnancy test for all other timepoints in CRU and OP.

<sup>c For the Day 85 Visit, dispense a urine pregnancy test kit for the Day 113 Follow-up Phone Call. For an ET Visit, dispense urine pregnancy test kits to allow monthly testing for 3 months after the last dose.

<sup>d Participants will be requested to take a urine pregnancy test at home at approximately Day 113, or, if ET, monthly for 3 months after the last dose; the site will solicit results, along with adverse events and concomitant medications, via phone call.

<sup>e Full PE at screening and symptom directed PE thereafter.

<sup>f Fasting, due to lipid panel. Note: lipid panel is not performed at Screening.

<sup>g Visit window (hours) is not applicable for urinalysis.

<sup>h Including temperature, respiratory rate, and pulse oximetry.

Abbreviations: ADA = antidrug antibodies; BMI = body mass index; CIC = circulating immune complexes; CRU = Clinical Research Unit; ECG = electrocardiogram; ET = early termination; FcRn = neonatal crystallizable fragment receptor; h = hours; ICF = informed consent form; Ig = immunoglobulin; NA = not applicable; OP = outpatient; PD = pharmacodynamic(s); PE = physical examination; PK = pharmacokinetic(s); WOCBP = women of childbearing potential.

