<sup>d Serum pregnancy test at Screening and Day -1 and urine pregnancy test for all other timepoints in CRU.

<sup>e All participants must be vaccinated as described in Section 6.5.3.

<sup>f Full PE at screening and symptom directed PE thereafter.

<sup>g Height and BMI at Screening only.

<sup>h Fasting, due to lipid panel. Note: lipid panel is not performed at Screening.

<sup>i Visit window (hours) is not applicable for urinalysis.

<sup>j Including temperature, respiratory rate, and pulse oximetry.

<sup>k In the event of an IRR, it is recommended to collect a blood sample for assessment of tryptase, histamine, CRP, cytokines, and complement as soon as the IRR is observed (prior to administering any IRR medication), and 2 hours, 24 hours, and 7 days (prior to the next dose of study drug) after onset of the IRR; a sample for PK/PD and ADAs may be collected if there is no predefined sample collection on the same day.

<sup>1 IRR evaluation will continue until the reaction is fully resolved.

Table 5: SoA – Day 14 through 28 for Multiple-Dose Cohort 3

Study Day	14		15		16 a	21			22			23	24	25	26	27	28
Assessments	Admit	Pre- dose	EOI	2 h b	24 h b	Admit	Pre- dose	EOI	2 h b	4 h b	12 h b	24 h b	48 h	72 h	96 h	120 h	144 h
Window (hours)		NA	+0.25	±0.25	±1		NA	+0.25	±0.25	±0.5	±0.5	±1	±1	±1	±1	±1	±1
Status (OP or CRU)									CRU								
Pregnancy test (WOCBP) c	X					X											
Alcohol breath test	X					X											
Urine drug screen	X					X											
Physical examination d		X					X							X			
Weight		X					X										
Study drug administration		X					X										
PK blood sampling		X					X		X	X	X	X	X	X	X	X	X
PD blood sampling - IgA, IgM, IgG		X					X		X	X	X	X	X	X	X	X	X
PD blood sampling - IgG subtypes 1-4		X					X		X	X	X	X	X	X	X	X	X
PD blood sampling – CIC		X					X		X	X	X	X	X	X	X	X	X
Immunogenicity blood sampling - ADA		X															
FcRn occupancy		X					X		X		X	X	X	X		X	
Biochemistry e,f	X					X								X			
Hematologye	X					X						X		X			
Exploratory biomarker sample														X			
Urinalysis g	X					X						X		X			1
Vital signs h	X	X	X	X	X	X	X	X	X	X	X	X	X	X	X	X	X
12-lead ECG (triplicate)		X					X		X	X	X	X	X	X	X	X	X

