#### 2.3.3. Overall Benefit: Risk Conclusion

ALXN1830 was well tolerated after single doses up to 30 mg/kg IV and 1250 mg SC (the highest single doses tested in SAD studies) in healthy adults. Also, ALXN1830 was well tolerated after multiple IV doses at 10 mg/kg × 5 doses in autoimmune patients. However, at multiple IV doses of 20 mg/kg in healthy participants, the development of potentially immune mediated IRRs that resulted in immediate and permanent discontinuation of study drug, together with 100% incidence rate of headache, suggested that close safety monitoring and implementation of risk mitigation measures are warranted for future studies in the clinical development program (Section 10.6). Of note, these IRRs were mild and moderate in severity and all resolved after cessation of the study drug, without treatment. Similarly, all AEs of headache were mild to moderate and were resolved.

As described in Section 2.1, potential impurities in the drug product could possibly have confounded the safety profile. Alexion has implemented changes to the manufacturing process for the current and future batches to enhance the control and detection of impurities.

The proposed safety measures in this study include documentation of pneumococcal and current seasonal flu vaccination; staggered dosing; stopping rules; close participant monitoring through 60 days after the last dose; close safety and PD monitoring with an unblinded medical monitor; avoidance of participants with a high risk of infections; antibiotics to manage infection as needed; rescue measures such as IVIG replacement in an extremely unlikely event of profoundly low IgG; as well as use of an SRC for safety monitoring and dose selections.

Considering the measures taken to minimize risk to participants in this study, the risks associated with ALXN1830 are justified by the anticipated benefits that may be afforded to patients with autoimmune disease.

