#### 8.8. Biomarkers

Whole blood for assessment of exploratory biomarkers will be collected as per the SoA (Section 1.3). Residual PK/PD samples may also be used for exploratory analyses.

In the event of an IRR, it is recommended to collect a blood sample for assessment of tryptase, histamine, C-reactive protein, complement, and cytokines as soon as the IRR is observed (prior to administering any IRR medication), and 2 hours, 24 hours and 7 days (prior to the next dose of study drug) after onset of the IRR.

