## 8.9. Immunogenicity Assessments

Samples for immunogenicity should be collected at times specified in the SoA (Section 1.3). Assays for the determination of human antidrug (anti-ALXN1830) antibodies (ADA) will be performed. All samples that are positive in a screening assay will be confirmed for antibody specificity and further characterized for titer. All samples that are confirmed positive for ADA will be evaluated for the presence of neutralizing antibodies. Other analyses may be performed to verify the stability of antibodies to ALXN1830 and/or further characterize the immunogenicity of ALXN1830.

In the event of an IRR, a sample for PK/PD and ADAs may be collected if there is no predefined sample collection on the same day.

The detection and characterization of antibodies to ALXN1830 will be performed using a validated assay method by or under the supervision of Alexion.

Participants found to have anti-ALXN1830 antibodies still present at the end of the study will be requested to return to the clinic for up to 1 year (from the first drug administration) or until ADA titers return to baseline levels (whichever occurs first). The follow-up visits are to be scheduled at 90-day intervals for blood collection to assess ADA.

Detailed instructions on the procedure for collecting, processing, storing, and shipping serum samples for immunogenicity analysis will be provided in the laboratory manual.

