7.2. Key Definitions

End of Study (EOS)

The EOS for each participant is defined as the date the last participant completes the last visit as shown in the Schedule of Activities in Section 1.3 of the Protocol.

Trial day

If the event date \geq date of first dose of IP, trial day = event date – date of first dose of IP + 1. If the event date < date of first dose of IP, trial day = event date – date of first dose of IP.

Nominal Time

Nominal time is the scheduled measurement time relative to time 0. Time 0 is the time of start of study drug dosing on Day 1.

Baseline Value

Baseline value will be defined as the last non-missing value recorded prior to first intake of study treatment.

Change from Baseline (CFB)

Sponsor: Alexion Pharmaceuticals, Inc.; Protocol No.: ALXN1830-HV-108

CFB = Post-baseline value - Value at baseline

7.3. **Missing Data**

For participants who are withdrawn from the study prior to the end of the study, all data collected up to the point of discontinuation will be used for analysis. There will be no imputation for missing data, unless otherwise specified.

7.4. **Visit Windows**

If there are multiple planned assessments for any study procedure at a given time point the latest nonmissing value will be used for summarization. Unscheduled assessments will be listed and will be used to flag baseline visit if this is the last non-missing assessment before the first dose of study drug, but unscheduled assessments will not be included in the summarization.

Pooling of Centers 7.5.

Not Applicable.

7.6. **Subgroups**

Not Applicable.

8. Participant Disposition, Demographic, Other Baseline Characteristics and Medication

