Laboratory parameter values will be graded according to the National Cancer Institute Common Terminology Criteria for Adverse Events (CTCAE).

All summaries will be based on results in SI (standard international system of units) units and will be

output in the order listed above.

Toxicity grading following the NCI CTCAE grades version 5.0 will also be derived for laboratory variables where applicable (see list below). Note, where gradings require investigator/clinical input, this will not be considered and only the numeric criteria will be used for the assignments. If this results in the criteria for more than one grade being met, the highest (worst) CTCAE grade will be assigned. For creatinine only, the criteria based on the upper limit of normal (ULN) will be used (changes compared to the baseline value will not be used), eg, CTCAE defines Grade 1 as > ULN - 1.5 x ULN or > 1 - 1.5 x baseline. Only the ULN – 1.5 x ULN criterion will be used (and not the baseline criterion).

The following parameters are CTCAE gradable:

- Clincal Chemistry: Alanine aminotransferase albumin, alkaline phosphatase, aspartate aminotransferase, total bilirubin, creatinine, gamma-glutamyl transferase, glucose (only do the grading the hypoglycemia, no grading for hyperglycemia), creatine kinase.
- **Hematology**: Absolute neutrophil count (neutrophil), total leukocytes (Leukocytes), hemoglobin (only do the grading for anemia, no grading for hemoglobin increased), platelet count, lymphocyte.
- Coagulation:International normalized ratio.

Actual values and changes from baseline in clinical chemistry, hematology and coagulation, will be summarized by treatment.

Shift tables for clinical chemistry, hematology, and coagulation from baseline CTCAE toxicity for each visit and to the maximum grade on treatment for each parameter will be provided. Participants with both a non-missing baseline and at least one non-missing post-baseline grade will be included in the shift tables. Unscheduled data will be included in the worst case across all scheduled and unscheduled visits after the first dose of study treatment. This means that if there are CTCAE grades derived from both unscheduled and scheduled visits data per test per participant then the highest grade will be summarized.

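### ADA sampling at an infusion-related reaction is optional, no ADA sample is scheduled on a third to a half of multiple-dose dosing days, and the SAP's general rule on unscheduled data would keep such a result out of the ADA summaries

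*Protocol*

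**What the plan says.** The footnotes to the infusion-site row in Protocol Section 1.3 cover blood sampling at an IRR. Under Tables 2, 10 and 11, after listing the marker panel, they add that "a blood sample for PK/PD and ADAs may be collected if there is no predefined sample collection on the same day". Tables 4 to 8 (Cohort 3) carry the same text without the word blood, and Protocol 8.9 repeats it: "In the event of an IRR, a sample for PK/PD and ADAs may be collected", on the same condition. For the marker panel the language is firmer. Protocol 8.8 states that "it is recommended to collect a blood sample for assessment of tryptase, histamine, C-reactive protein, complement, and cytokines as soon as the IRR is observed". Table 13 names ADA-associated IRR as a risk and points to the schedule and Section 10.4, but Section 10.4 does not mention ADA sampling.

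In the SAP, Section 7.4 (Visit Windows) says that unscheduled assessments are listed and can serve to flag baseline, but "unscheduled assessments will not be included in the summarization". Section 12.2 departs from this for the laboratory shift tables: "Unscheduled data will be included in the worst case across all scheduled and unscheduled visits after the first dose of study treatment". Section 11 contains no such sentence. Section 11.1.2 names incidence, titer, duration and time to detection without saying which samples count. Incidence of ADA and neutralizing antibodies (NAb) is a secondary endpoint.

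**The concern.** The question of whether a reaction is antibody-driven matters in this programme. Protocol 2.3.3 refers, for the multiple 20 mg/kg IV doses, to "the development of potentially immune mediated IRRs that resulted in immediate and permanent discontinuation of study drug". The ADA result closest to a reaction bears most directly on that question. Under this plan it may not be drawn. If it is drawn, the general summary rule would leave it out of a secondary endpoint.

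Participants with reactions are also those most likely to have fewer later samples. The early-termination visit in Protocol 7.3 is to be held if possible. Section 10.4, on participants who stop after a severe reaction, asks for the scheduled safety, PK and PD evaluations and does not name immunogenicity.

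**Working it through.** The plan gives no figure to reproduce here, so the check is a count from the schedule followed by a reading of the SAP rules.

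**1. Dosing days without a scheduled ADA sample** (ADA row against study-drug row, Tables 2 and 4 to 11):

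| Cohorts | Doses | Predose ADA on dosing days | No ADA on dosing days | Share |
|---|---|---|---|---|
| 1 and 2 | 1 | 1 | none | 0/1 |
| 3 | 12 | 1, 15, 29, 43, 50, 57, 64, 71 | 8, 22, 36, 78 | 4/12 = 33% |
| 4 to 6 | 4 | 1, 15 | 8, 22 | 2/4 = 50% |

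Protocol 8.3.5.1 places IRRs during infusion or within hours, at most 24 hours later, so the dosing day is the relevant day.

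**2. Distance to the neighbouring samples on the uncovered days.**
- Day 8: Days 1 and 15 (8 − 1 = 7; 15 − 8 = 7).
- Day 22: Days 15 and 29 (7 and 7).
- Day 36: Days 29 and 43 (7 and 7).
- Day 78: Days 71 and 85 (7 and 7).

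The later sample always precedes any further dose. Days 15 and 43 are predose. Day 29 is predose in Cohort 3 and 168 hours after the last dose in Cohorts 4 to 6. Day 85 is 168 hours after the last dose in Cohort 3. Even so, a positive 7 days after a reaction cannot show that antibody was present at the reaction.

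**3. The condition attached to the option.** The footnote does not say which predefined sample closes the option. PK and PD are drawn predose on every dosing day. If any of these counts, the optional ADA sample is never triggered on a dosing day. If only a predefined ADA sample counts, it is available on the days in the last column but one of the table.

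**4. What happens to a result that is drawn.** Take a Cohort 4 participant who is ADA-negative on Day 1, reacts on Day 8 and tests positive in the optional sample. Apply SAP 7.4 as written:
- Day 15 positive: the participant counts in incidence, but first detection is Day 15 instead of Day 8, which is 7 days late.
- All of Days 15, 29, 50, 64 and 85 negative or missing: no positive result is summarized.
- No sample after Day 8: the Immunogenicity Set (SAP 6.5) needs only a predose and one postdose sample, so the participant enters the denominator while the positive stays out of the numerator.

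In Cohort 3 the corresponding scheduled postdose samples are Days 15, 29, 43, 50, 57, 64, 71, 85, 99, 120 and 141, 11 in all.

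**5. Size per affected participant.** With 6 planned active participants, 1/6 = 16.7 percentage points, and two give 2/6 = 33.3. Pooled over Cohorts 3 to 5 (3 × 6 = 18), 1/18 = 5.6 points. The documents do not give the number affected. If there are none, the change in incidence is 0.

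**The case against.** The strongest reply is that SAP 7.4 was not written with ADA in mind. It stands under visit windows, and the sentence before it chooses one value per time point, so it can be taken as a rule for by-visit summaries only. ADA incidence is a participant-level result. Where SAP 9.2 groups PK parameters by ADA status, it does so by whether any result is positive, with no limit to scheduled samples, and the Immunogenicity Set has no such limit either. This stands to the extent that exclusion is the result of applying a general rule and is not said of ADA in terms. It does not settle the matter, because the SAP wrote out an exception for laboratory worst cases and none for ADA.

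The result is also not lost. It is listed, and the individual plots of PK, PD, ADA titer and NAb in SAP 11.1.2 can show it. With six active participants per planned cohort and no hypothesis test, participant-level display is a fair way to examine a link between ADA and reactions. That also stands. Drug concentration is less exposed than ADA, since PK is drawn predose at every dose and at 2, 4, 12 and 24 hours after the Day 22 and Day 78 doses.

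A reader might go further and infer that the draw ought to be compulsory. The marker panel is itself only recommended. Section 10.4 counts common symptoms such as headache among the possible signs, so a compulsory draw could be triggered often, and the amendment history records that Amendment 3 cut blood volume in the multiple-dose cohorts. The case for a compulsory draw is therefore weak.

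**Conclusion.** The concern holds in a limited form. ADA sampling at an IRR is optional, and no ADA sample is scheduled on 2 of 4 dosing days in Cohorts 4 to 6 or 4 of 12 in Cohort 3. SAP 7.4, applied as written, would keep a reaction-triggered result out of ADA incidence, titer and time to detection. The effect on incidence is confined to participants whose scheduled postdose samples are all negative or missing. For the others, first detection is up to 7 days late, assuming the reaction falls on the dosing day and the next scheduled sample is taken and positive. The more general loss is that the link between ADA and the reaction appears only in listings or individual plots.

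Two stronger readings are tempting and not supported. One is that the SAP expressly bars these results from incidence; it does not, and SAP 9.2 leaves room for the opposite view. The other is that the sample 7 days later is confounded by a further dose; on all the days named it is drawn before one. On the remaining dosing days a predose ADA sample gives the status just before the reaction. Since Cohort 6 enrolled nobody, the four-dose cohorts actually affected are Cohorts 4 and 5.

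**What to change.** 1. **SAP 7.4 and 11.1.2.** State that ADA and NAb incidence, titer and time to detection use all postdose results, scheduled or unscheduled, including those triggered by an IRR. Add a listing of ADA status beside each IRR. This costs two or three sentences and one listing. Because the study ended early, this is the part that affects data already collected.

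2. **Protocol 1.3 footnotes and 8.9.** Give the ADA sample at IRR onset at least the recommended status of the marker panel, taken in the same draw. State that the condition about a predefined sample refers to a predefined ADA sample, since PK and PD are drawn predose on every dosing day. This costs one small extra tube per reaction in participants who react, and nothing for the others. With dosing ended, its use is mainly for later studies that reuse this text.
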